changes in blood pressure or reported dizziness/lightheadedness we will hold off on lofexidine dosing, hydrate the participant and repeat blood pressure after 30 to 60 minutes to determine how long the lofexidine dose will be held. If vital signs and reported side effects return to normal ranges lofexidine dose will be continued as per protocol. If vital signs and reported side effects remain lofexidine medication will be held until the next study visit. We will counsel all participants in the importance for adequate oral hydration during the consent process and throughout the study.

Participants will be monitored by clinical staff frequently, with vital signs checks and withdrawal assessments. Starting day 1 participants will be sent home with ancillary medications (clonazepam, zolpidem) and will be instructed that they may use ancillary medication if needed.

Ancillary medications: A standing order of additional medication targeting withdrawal symptoms will be available to patients and will include clonazepam 1 mg tid and zolpidem 10 mg QHS. Ancillary medications will be offered daily during the induction week and will include clonazepam to reduce anxiety and dysphoria, and zolpidem for insomnia. Participants will be provided take-home doses of ancillary medications in small doses and on a tapering schedule for two weeks (after the detoxification week) to alleviate any protracted opioid withdrawal. Additional doses will be offered as clinically determined for participants experiencing continued withdrawal symptoms.

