Naloxone challenge and Vivitrol injection: The purpose of the naloxone challenge is to determine if the participant is likely to tolerate a Vivitrol injection. The timing of naloxone challenge is based on a number of clinical factors including time since the last opioid use, pattern of recent opioid use, severity of tolerance and withdrawal symptoms, and response to ancillary medications used for the treatment of withdrawal. We will make the decision to administer naloxone on the COWS score, as well as the other factors noted above. The COWS score may be suppressed by other medications, and could also be suppressed by use of opioids. Therefore a global assessment of the participant's progress through the induction period will be taken into account when deciding to administer naloxone, using the COWS as the final indicator of readiness. **If a participant reports continued use of opioids, then naloxone challenge will not be administered because it would be very likely to precipitate withdrawal. However, if the urine test for opioids is positive, but the patient reports not having used any opioids in the recent days, then clinical judgment will be exercised as to whether to administer the naloxone challenge. This judgment would balance the risk of a brief episode of withdrawal precipitated by naloxone, against the potential benefit that the patient passes the naloxone challenge (no exacerbation of withdrawal symptoms) can receive injection naltrexone.**

Once a participant has a COWS < 6, they qualify for a naloxone challenge. Discussion of the naloxone challenge risks/benefits will be discussed with study staff and the naloxone consent form will be signed prior to the challenge. The challenge will be conducted over a 60 minute time frame. Individuals will be asked the last opioid use, route, and amount. A naloxone dose of 0.8mg will be given as an injection in the participants upper arm muscle. Participants will then be monitored for withdrawal and changes in vital signs for the next 60 minutes using the standard COWS (5 minutes, 20 minutes, and 60 minutes after naloxone dose). Once the participant completes the naloxone challenge and has no increase in COWS withdrawal score ≥ 10 they may receive XR-naltrexone injection (Vivitrol 380mg) on Day 2-10. Following the naltrexone injection, the patient will be required to remain at the clinic for at least 1 hour prior to discharge, to monitor for any increased withdrawal symptoms or side effects.

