Please create or insert a table describing the proposed collection of blood or other biological specimens

Approximately 10 cc of blood is drawn at baseline for blood chemistries, CBC, and pregnancy (females).

Urine will be collected at each study visit.

Assessment Instruments

Create a table or give a brief description of the instruments that will be used for assessment

Assessment of Drug Abuse Severity

Clinical Global Impression Scales for Substance Abuse: This is a clinician-rated and self-rated instrument that rates global severity and improvement on 7-point scales for opioid use. On the improvement scale a rating of 1 = "very much improved" requires abstinence, and a rating of 2 = "much improved" requires at least a 75% reduction in substance use since beginning study medication. The opioid change score is dichotomized such that patients scoring 1 or 2 are rated "responders" and all others "non-responders." A similar approach will be used to assess severity and improvement for global symptoms weekly by the study physician.

Timeline Follow-back (TLFB) Assessment: The Timeline Follow-Back method will gather self-reported opioid use data for each day during the 28 days prior to study enrollment and each day during the study period. Other substance (including nicotine and alcohol) use self-report data will also be gathered during the TLFB interview.

Urine Drug Testing: A urine sample will be collected under direct observation at each visit.

Craving Visual Analog Scale: A visual analog scale is used for patients to rate the intensity of craving for opioids experienced since the previous visit.

Clinical Opiate Withdrawal Scale (COWS): The COWS is a 11-item scale reliably eliciting severity of common physical and psychological symptoms of opiate withdrawal (Wesson, 2003). It will be used to examine occurrence of symptoms of opioid withdrawal and will be collected at each visit.

Miscellaneous Measures

Hamilton Depression Scale (HAM-D): In addition to mood symptoms, the HAM-D has items that measure anxiety, low appetite, irritability, and insomnia, which are symptoms of subacute opioid withdrawal of particular interest for this study (Hamilton 1960).

Assessment of Side Effects and Medication Compliance

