Systemic Assessment for Treatment Emergent Events (SAFTEE): The psychiatrist or research nurse queries the patient and logs side effects and other treatment emergent events since the past visit, recording severity, action taken, and whether the side effect(s) is continuing or resolved.

Assessing Medication Compliance: (1) The study psychiatrist during each weekly evaluation queries and records patients' self-reported compliance and missed doses. (2) Compliance is also monitored with pill counts conducted by the research nurse.

Reporting of Adverse Events

All adverse events (AE) reported by the participant or observed by the investigator will be individually listed on the Adverse Event Form (SAFTEE). The signs and symptoms, time of onset, duration, severity, medical intervention, follow-up procedures, and suspected relationship to study drug will be reported. Any AE (clinical signs and symptoms or laboratory test) associated with the use of study drug, whether or not considered drug related, will be documented by the study psychiatrist.

All AEs reports will be reviewed by the study physicians and PI. In the event of any "serious" and/or "unexpected" adverse drug experiences, the PI will notify the Psychiatric Institute IRB and the study sponsor, US WorldMeds.

Please see table of study assessments for complete detail of assessments.

Please attach copies, unless standard instruments are used
study assessments.pdf

Off label and investigational use of drugs/devices

Choose from the following that will be applicable to your study

Research Related Delay to Treatment

Will research procedures result in a delay to treatment?

Yes

Maximum duration of delay to any treatment

Active treatment of known efficacy (induction onto Vivitrol) begins when patients have signed study consent and begin outpatient treatment at STARS. A delay of up to 2 weeks is possible prior to enrollment.

Maximum duration of delay to standard care or treatment of known efficacy

The maximum delay is up to two weeks. Screening, diagnostic and medical evaluation to determine eligibility are generally completed within 3 to 5 days. It may take another week to complete a longer evaluation (for example if input is needed from another treating physician), or for patients to arrange to be

absent from work or family responsibilities. Clinical staff are in regular contact with patients during this time, and patients are informed of other treatment options available in the community.

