Baseline demographics and non-efficacy outcomes, including retention, frequency of adverse events, and receipt of the first injection of naltrexone-xr will be tabulated and summarized for this open-label treatment group using means, standard deviations and percentages where appropriate. Opioid use (Timeline Follow-Back), craving for opioids (VAS scale), urine toxicology, and depression scores (HAMD) during detoxification and post detoxification will also be analyzed using similar models as in the primary hypothesis. PROC GLIMMIX in SAS® 9.4 will be used to conduct all analyses. All statistical tests will be two-sided with a level of significance of 5%.

Hypotheses testing:

Primary Hypothesis: Lofexidine will be associated with reduced symptoms of opioid withdrawal during the 2-10 days induction phase as compared to baseline (day 1).

To analyze the primary hypothesis, withdrawal severity (COWS) during the 2-10 days induction phase will be summarized using descriptive summaries and analyzed using longitudinal generalized linear mixed effects models with a main effect of time, adjusted by the baseline (day 1) withdrawal score. Based on the distribution of the outcome corresponding link function will be used (eg. log for skewed data etc). A random intercept will be used to account for the between subject variances and an autoregressive (AR1) covariance structure to account for the correlation of the repeated observations within subjects over time.

Secondary Hypotheses: Lofexidine used to manage opioid withdrawal symptoms will result in successful initiation of outpatient naltrexone-XR treatment by the completion of the induction phase and patients receiving first naltrexone-xr injection.

To analyze the secondary hypothesis, the proportion of subjects who complete the induction phase and receive the first naltrexone-xr injection will be calculated. A one-sample proportion test will be used to compare whether the sample proportion is significantly different from benchmark proportions of successful induction to naltrexone-xr. Additionally, 95% confidence interval will be computed to estimate the expected range of population proportion of successful induction.

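### With one arm, and clonazepam and zolpidem offered alongside lofexidine from Day 1, the COWS and induction results can be credited to the regimen but not to lofexidine

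*Combined protocol and SAP*

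**What the plan says.** Both hypotheses in the Overview of Data Analytic Plan name lofexidine and no other drug. The primary is "Lofexidine will be associated with reduced symptoms of opioid withdrawal during the 2-10 days induction phase", with Day 1 as the reference. The secondary is "Lofexidine used to manage opioid withdrawal symptoms will result in successful initiation of outpatient naltrexone-XR treatment", measured by completion of induction and receipt of the first injection.

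The primary model for COWS has time as its main effect, adjusts for the Day 1 score, and uses a random intercept with an AR(1) structure. HAM-D, craving, urine toxicology and opioid use are to be analysed with similar models. The secondary analysis tests the observed proportion against benchmark proportions that are neither given nor sourced.

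Study Procedures describes what participants receive. Lofexidine starts on Day 1, and so does the instruction to abstain from opioids. From the same day participants take home ancillary drugs to use if needed. The standing order, directed at withdrawal symptoms, "will include clonazepam 1 mg tid and zolpidem 10 mg QHS". It is offered daily in the induction week: clonazepam for anxiety and dysphoria, zolpidem for insomnia.

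The section on the naloxone challenge states: "The COWS score may be suppressed by other medications, and could also be suppressed by use of opioids".

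**The concern.** The hypotheses make a statement about one drug, but the data come from people offered three drugs from the same day, with no comparison group. If the plan is followed as written, a favourable COWS trend or induction rate would be reported as a lofexidine result when some or all of it could come from the ancillary drugs, from continued opioid use or from the natural course of withdrawal.

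The protocol itself recognises that COWS can be suppressed in this way and tells clinicians to allow for it when judging readiness for naloxone. The analysis plan makes no matching allowance. What is at stake is the wording of the trial's main conclusion, and whether a later study could rely on it as evidence about lofexidine.

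**Working it through.** The documents state no power, effect size or standard deviation, so there is no figure to reproduce. The check is one of identifiability, followed by a comparison of sections.

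**1. What the COWS data can identify.** Let post = 0 at the Day 1 baseline and 1 afterwards. Code lofexidine (L) and ancillary availability (A) as what is offered to everyone:

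- intercept = 1
- time T = post
- L = post
- A = post

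The last three columns are identical, so the design matrix has rank 2 for 4 coefficients, and

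E[COWS] = b0 + (bT + bL + bA) × post.

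Only the sum bT + bL + bA is estimable. The lofexidine part bL is not.

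**2. Would recorded intake rescue it?** Suppose A is replaced by tablets actually taken, which vary because use is as needed. A then has its own column and the rank rises to 3 of 4, but L and T remain identical, so bL is still tied to the time course. In addition, bA would be biased because people in worse withdrawal take more. Lofexidine intake can also vary, because doses are held for dizziness or low blood pressure, but that variation follows clinical state and gives no clean contrast.

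**3. The secondary endpoint.** The sequence in Study Procedures is: COWS below 6, then naloxone challenge, then first injection. Anything that lowers COWS can help a participant qualify for the challenge. The secondary result therefore shares the attribution problem. The benchmark offers no way out: with no value or source, nothing shows that its patients had the same ancillary drugs without lofexidine.

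**4. HAM-D.** Assessment Instruments singles out HAM-D because it has "items that measure anxiety, low appetite, irritability, and insomnia". Two of these, anxiety and insomnia, are the stated targets of clonazepam and zolpidem.

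**5. What is recorded.** Under Assessing Medication Compliance, the study psychiatrist "during each weekly evaluation queries and records" self-reported compliance and missed doses. Nurse pill counts are a second source, but neither their frequency nor the tablets they cover are stated. Visits in the detoxification period are daily. The assessment schedule is an upload that is not in the text available. The supportable statement is that no visible section specifies daily recording of ancillary intake, and that the analysis plan does not use or summarise it.

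**The case against.** The strongest case against is that this is an open-label pilot whose only listed aim is safety and tolerability, that co-medication is openly described, and that the primary hypothesis speaks of association. This lowers the stakes, but it does not cover the secondary hypothesis, which is causal, or the choice to test drug-specific hypotheses at the 5% level.

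A reader might infer four stronger things. The documents do not support them.

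- **That the false-positive rate for a lofexidine effect can be quantified.** Any such figure needs an ancillary effect, a standard deviation of change and a counterfactual course, and none is given. Withdrawal might rise after Day 1, since participants have opioid-positive urine at consent and are only then told to stop. A paired test against Day 1 is also not the planned analysis. With Day 1 as a covariate, the natural reading is that the time effect compares later days with one another, and a constant ancillary shift would add nothing to it. If Day 1 is also kept as an outcome, a shift would register. The plan does not settle which.
- **That the protocol says clonazepam and zolpidem suppress COWS.** It refers to other medications generally. Including these two is a fair inference, because the same paragraph mentions ancillary drugs used for withdrawal and these are the only ones named, but it remains an inference.
- **That ancillary doses cannot be placed by day.** The pill counts might allow it, and the assessment schedule cannot be seen.
- **That adverse events from sedatives will be tabulated as lofexidine events.** Safety outcomes "will be tabulated and summarized for this open-label treatment group", and the adverse event form already records onset and suspected relationship to study drug.

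**Conclusion.** The point holds as one of attribution. In this single arm, a change in COWS or HAM-D, or an induction proportion, supports a conclusion about lofexidine given with as-needed clonazepam and zolpidem during early abstinence. It does not support a conclusion about lofexidine itself, and the hypotheses as worded go further than the design allows.

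This rests on the single arm and the shared Day 1 start, both explicit, and on the inference that the ancillary drugs are among the medications able to lower COWS. Its numerical size is unknown and cannot be derived from the documents. The change is worth making because it alters what the trial may conclude, at little cost, and leaves the safety and tolerability aim intact.

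**What to change.** 1. Reword the primary and secondary hypotheses and the planned conclusion to refer to the lofexidine-based regimen (lofexidine with clonazepam and zolpidem as needed), and state that no lofexidine-specific effect will be claimed.
2. Specify that clonazepam and zolpidem tablets taken since the previous visit are recorded at each daily induction visit, using the existing pill counts. If the assessment schedule already requires this, cite it in the analysis plan.
3. Report COWS, HAM-D, and dizziness or sedation events by day or visit beside ancillary intake. Keep this descriptive: use follows withdrawal severity, so adjustment would not remove the confounding.

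The cost is revised wording, one tablet count at visits that already take place, and a weaker, regimen-level claim. No change to arms, visits, treatment or sample size is needed.

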Screening for this study will be covered by the Substance Treatment and Research Service (STARS) umbrella screening protocol #6582R (PI: [name]). Trained research assistants and administrative assistants under the supervision of the principal investigator conduct the initial phone screening. Under protocol #6582R, patients who contact STARS interested in research trial participation are informed that they will be asked questions of a personal nature and asked to provide verbal consent for such questions. A "phone screen" form is completed by the phone screener, which asks basic demographic information, contact information (for scheduling purposes) and description of substance use to determine whether an in-person evaluation appointment is appropriate. Individuals are also informed that if they make an initial screening appointment this "phone screen" information will be forwarded to the clinician to facilitate the first meeting.

Inclusion/Exclusion Criteria

Name the subject group/sub sample

Adults with current Opioid Use Disorder

Create or insert table to describe the inclusion criteria and methods to ascertain them

1. Individuals between the ages of 18-60 (clinical interview)
2. Meets DSM-5 criteria of current opioid use disorder present for at least six months, supported by a positive urine for opioids on day of consent (MINI interview, Clinical interview, and urine toxicology)
3. Seeking treatment for opioid use disorder (Participant self-report, MINI interview, Clinical interview)
4. Capable of giving informed consent and complying with study procedures (clinical interview)
5. History of opioid withdrawal (MINI interview, Clinical interview)

Create or insert table to describe the exclusion criteria and methods to ascertain them

- 1) Meets DSM-5 criteria for substance use disorder other than opioid as the primary diagnosis (clinical interview)
- 2) Having a comorbid psychiatric diagnosis that might interfere with participation or make participation hazardous, such as an active psychotic disorder or current suicide risk (clinical interview)
- 3) Methadone maintenance or long-acting agonist (buprenorphine) treatment (self-report; urine toxicology)
- 4) Buprenorphine maintenance treatment (self-report; urine toxicology)
- 5) Known history of allergy, intolerance, or hypersensitivity to candidate medication (lofexidine, naltrexone, naloxone) (clinical assessment)

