The study will be entirely outpatient. Upon study entry, participants will begin clinic visits at the Substance Treatment and Research Service (STARS) clinic. After the detoxification period (2-10 days) where participants will attend the clinic daily, participants will then attend the clinic twice per week for the next 4 weeks and then once per week for the last 4 weeks. All participants will visit the clinic weekly to provide urine toxicology, report on adverse events, and complete additional assessments. All participants will also receive medical management, a medication adherence focused psychosocial intervention that facilitates compliance with study medication and other study procedures, and promotes abstinence from opioids and other substances.

Detoxification and Induction onto Injectable Naltrexone: The detoxification-naltrexone induction will be performed at the STARS outpatient research clinic, which is outfitted with a detoxification suite. After study consent and prior to initiating any study procedures, a urine will be collected and tested for pregnancy. A negative urine pregnancy is required at admission as detoxification and naltrexone treatment would not be recommended during pregnancy.

Participants come to the clinic daily for safety assessments, clinical monitoring, and management of withdrawal. Patients will be seen at the clinic preferably in the morning on Day 1 to initiate the lofexidine-naltrexone procedure. On Study Day 1, following the consent procedure, participants will start lofexidine and will be instructed to begin to abstain from opioids. Vital signs will be checked post 1 hour of initial lofexidine dose to see if there is an effect on blood pressure. Participants will continue to receive lofexidine 0.18mg #3 QID (approximately 9am, 1pm, 5pm, 10pm). Administration of lofexidine is withheld in case of dizziness or lightheadedness complaints, low blood pressure (SBP < 90 or DBP < 60), or orthostatic blood pressure changes (from lying down to standing up drop of SBP \geq 20 mmHg, DBP \geq 10 mmHg). If there are

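### The primary hypothesis compares induction COWS with Day 1, but the planned model does not estimate that change or link COWS to opioid use, and COWS after the injection has no planned summary

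*Combined protocol and SAP*

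**What the plan says.** The primary hypothesis in the Overview of Data Analytic Plan is that "Lofexidine will be associated with reduced symptoms of opioid withdrawal during the 2-10 days induction phase as compared to baseline (day 1"). For the analysis, "withdrawal severity (COWS) during the 2-10 days induction phase will be summarized using descriptive summaries" and then fitted with a mixed model "with a main effect of time, adjusted by the baseline (day 1) withdrawal score", with a random intercept and AR(1) correlation. It has no term, stratification or companion table for opioid use.

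Opioid use is not left out of the plan. Timeline Follow-Back (TLFB) use heads a list of further outcomes, which continues: "craving for opioids (VAS scale), urine toxicology, and depression scores (HAMD) during detoxification and post detoxification will also be analyzed". COWS is not on that list, so its only planned analysis is within induction.

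Other sections supply the context:

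- **Inclusion criteria:** the diagnosis must be "supported by a positive urine for opioids on day of consent".
- **Detoxification and Induction:** on Day 1, after consent, "participants will start lofexidine and will be instructed to begin to abstain from opioids". COWS is taken at least twice a day, at the start and end of the visit.
- **Naloxone challenge:** COWS can be suppressed by opioid use and by other medications. Continued use is foreseen. A COWS below 6 qualifies a participant for the challenge, which adds scores at 5, 20 and 60 minutes.
- **Assessment Instruments:** TLFB covers each of the 28 days before enrollment and each study day. Urine and COWS are collected at every visit.
- **After induction:** "participants will then attend the clinic twice per week for the next 4 weeks". Lofexidine is tapered over 2-4 days after the injection, and ancillary medication is given "on a tapering schedule for two weeks (after the detoxification week) to alleviate any protracted opioid withdrawal". The risk section warns that the first Vivitrol dose could cause withdrawal.

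**The concern.** There are three linked gaps and one separate one.

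1. **Hypothesis and model differ.** With Day 1 as a covariate, the outcome days are Days 2-10 and the time effect describes change among them. A change from Day 1 needs its own contrast, and none is specified. Nor does the plan say which Day 1 score is baseline: one may precede the first lofexidine dose and another follow it.
2. **Opioid use can move the Day 1 comparison either way.** Use on later days lowers COWS and looks like relief. Recent use that suppresses the Day 1 score makes later days look worse. Without a link between use and COWS, a reader cannot tell which has happened.
3. **Leaving induction depends on the outcome.** A low score opens the way to the injection and so out of the window, which favours apparent relief.
4. **COWS after the injection has no planned summary.** The direct withdrawal measure is collected, but not reported, in the period for which the protocol itself warns of withdrawal. The Background adds that a shorter procedure may make withdrawal more severe.

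At stake is whether a result attributed to lofexidine reflects withdrawal, opioid use or timing.

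**Working it through.** The plan gives no COWS mean, SD, effect size or power, so there is no figure of its own to reproduce. Every size below rests on assumptions.

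**Assumptions.** No true change; latent COWS mean 12; SD 3 between and 3 within participants; AR(1) 0.5; COWS falls 6 points when opioids suppress it; 20 participants (the enrollment target); Days 1-10; 20,000 simulated trials per case. The test is a one-sample t test of each participant's mean over Days 2-10 minus Day 1, two-sided 5% (2.5% each way).

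**Expected error in the Day 1 contrast.** Error = 6 x (share suppressed on Day 1 - share of Day 2-10 days with use). With use on 20% of later days:

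| Suppressed on Day 1 | Expected error (points) | False relief | False worsening |
|---|---|---|---|
| 0% | 6 x (0 - 0.2) = -1.2 | 36% | 0% |
| 20% | 6 x (0.2 - 0.2) = 0 | 3% | 2% |
| 50% | 6 x (0.5 - 0.2) = +1.8 | 0% | about 41% |

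At n = 10 (the completer target) the first and last rows become about 19% false relief and 21% false worsening. With use on 10-40% of later days and a drop of 4-8 points, false relief runs from 8% to 98% with no Day 1 suppression, and false worsening from 7% to 75% with half suppressed.

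**Trend over Days 2-10.** Per-participant slopes give 2.4% and 2.6% error in the two directions when use is even. If use rises from 10% to 30% of days, a false fall appears in 18% of trials. If use falls by the same amount, a false rise appears in 18%.

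**Exit at COWS below 6.** Treating the first such score as the end of induction, with no Day 1 suppression, false relief rises from 36% to about 45% if days with use cannot end induction, and to about 69% if use goes unreported and they can.

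**Natural course.** A second illustration assumes untreated COWS of 2 at last use, 13 at two days and 3 at ten days, with n = 10 and the same exit rule. With no lofexidine effect and no later use, Day 1 at 48 hours after last use gives a mean change of -4.5. With a true 3-point benefit, Day 1 at 6 hours gives +3.9. Timing alone can set the sign.

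**Does excluding days with use repair it?** With no Day 1 suppression, every such day identified and use unrelated to severity, false relief drops from 36% to 2.5%. With 20% suppressed on Day 1, the same exclusion raises false worsening from 2% to about 23%; with 50%, from about 41% to about 84%. If people use on their worse days, the exclusion is biased even without Day 1 suppression (6-12% false relief).

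**COWS after induction.** Scheduled visits are 2 x 4 + 1 x 4 + 1 End-of-Study = 13, matching $260 / $20 = 13 in the compensation section. Detoxification has up to $200 / $20 = 10. So COWS from up to 13 of 23 scheduled visits has no planned summary. Twice-weekly visits give 2/7 x 2 = 0.6 to 2/7 x 4 = 1.1 visits per participant during the lofexidine taper, and 2/7 x 14 = 4 in two weeks. With SD sqrt(9 + 9) = 4.24, the 95% half-width t x 4.24 / sqrt(n) is 4.5 points with 6 observed, 3.0 with 10 and 2.0 with 20.

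**The case against.** The strongest reply is that this is a single-arm, open-label pilot with 10 completers required, that its hypothesis already speaks of association, and that COWS including days of use is a legitimate summary of the whole regimen. That stands, and is why the planned model can remain. It does not supply the missing Day 1 contrast.

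A reader might infer that the plan ignores opioid use. It does not: TLFB and urine are analysed during detoxification with similar models, so the level and course of use will be seen. Only the link to COWS is missing.

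A reader might also take 36% or 41% as the error rate of the planned test. Those figures belong to a Days 2-10 minus Day 1 contrast that the hypothesis wording invites but the plan does not specify. The planned time effect is distorted by use mainly if use changes over the days.

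On the period after the injection, it is fair to say that adverse event frequency, HAM-D and craving give indirect coverage, that the end-of-visit COWS on the injection day may fall within induction, and that scheduled visits during the lofexidine taper are few. These points limit what a summary can show. They are not a reason to leave the direct measure unreported.

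**Conclusion.** The point holds in limited form. The hypothesis names a change from Day 1 that the specified model does not by itself estimate. If that change is reported, opioid use and timing can bias it in either direction, and exit at a low COWS pushes it towards relief. COWS after detoxification is collected without a planned summary. These statements rest on the text.

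The sizes do not. They depend on assumed COWS means, SDs, suppression and use rates, and they apply to the Day 1 contrast. The documents do not show that bias will occur or which way it would go. Nor do they support treating exclusion of days with use as a correction: people opioid-positive at consent and only then told to abstain may well be suppressed on Day 1, and in that case exclusion makes the error worse.

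**What to change.** Amend the SAP only, using data already collected:

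1. Keep the planned model. Define baseline as the start-of-visit Day 1 COWS taken before lofexidine, and use one routine start-of-visit COWS per day. Keep the three scores after naloxone out of the model and report them separately. Report the mean of Days 2-10 minus Day 1, with a 95% confidence interval, beside the time effect.
2. Tabulate COWS by day and by same-day TLFB use, with the number of days with use and the number still in induction. Show Day 1 status including use on the day before, since use the previous night can suppress the Day 1 score. Keep this descriptive, and do not present an analysis without days of use as a corrected estimate.
3. Add a descriptive COWS summary aligned to the injection day and running through the lofexidine and ancillary tapers. Give numbers observed, and show unscheduled visits apart because they over-represent people with more withdrawal.
4. Word the conclusion as the course of withdrawal under the whole uncontrolled regimen, not as an effect of lofexidine.

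The cost is SAP wording and some tables, with no new visits or measurements. The drawbacks are sparse data after the injection, limited to injected participants, and small Day 1 subgroups.
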